1 PROTOCOL SUMMARY

1.1 SYNOPSIS

Title: A phase II study of talimogene laherparepvec (T-VEC) in the treatment of recurrent cutaneous angiosarcoma

Study Description: Seventy-five percent of cutaneous angiosarcoma (CA) patients will eventually fail systemic therapy, and relapsed/refractory patients are left with no known efficacious treatment options. We hypothesize that direct treatment of CA lesions with T-VEC will stimulate local antitumor response, leading to objective responses and prevention of recurrence among enough patients to make this a viable treatment option for the affected population.

Objectives:

Primary Objective: To evaluate the efficacy of T-VEC as treatment for relapsed/refractory cutaneous angiosarcoma

Secondary Objectives:

1. To establish duration of response among treated patients that demonstrate response
2. To measure the duration of progression-free survival among treated patients
3. To measure the complete response rate for lesions that have complete clinical regression following study treatment
4. To monitor adverse events following administration of T-VEC injections
5. To measure the rate of patients requiring surgical resection of T-VEC–treated lesions

Tertiary/Exploratory Objectives:

1. To measure the degree of immune infiltration in surgically resected T-VEC–treated tumors
2. To evaluate surgical outcomes for those patients whose T-VEC–treated tumors are resected

Endpoints:

Primary Endpoint: Overall response rate: the proportion of patients to demonstrate complete or partial responses in injected lesions per modified RECIST criteria appropriate for cutaneous neoplasms.

Secondary Endpoints:

1. Response duration will be measured from the time of initial partial response or complete response until documented progression

2. Progression-free survival: period from time of first injection to progression of disease or appearance of new cutaneous angiosarcoma tumors that were not present at the time of study entry
3. Complete Response rate: proportion of patients with CR, defined as lesions with complete clinical regression
4. Incidence of adverse events from injection of T-VEC into cutaneous angiosarcoma
5. Proportion of patients whose T-VEC–treated tumors require surgical resection

Tertiary/Exploratory Endpoints:

1. Immunohistochemistry and flow cytometry analyses of immune infiltration within resected tumor specimens
2. Surgical outcomes recorded will include margin status, percent viable tumor, postoperative complications, and disease-free interval following resection.

Study Population: Thirteen patients with locally advanced recurrent or unresectable cutaneous angiosarcoma

Phase: Phase II

Description of Sites/Facilities Enrolling Participants: Moffitt Cancer Center (Tampa, FL), a high-volume, NIH-designated Comprehensive Cancer Center

[figure not shown]
Description of Study Intervention: Patients will undergo intralesional injections of up to 4 cc of 10^6 plaque-forming units (PFU)/mL of T-VEC. Dose is dependent on the diameter of the lesions to be injected (volume injected is related to diameter of lesion(s) at time point 0). Three weeks later and every other week thereafter, the patients will be injected with up to 4 cc of 10^8 PFU/mL, with dose dependent on the diameter of the lesion(s) to be injected. Patients may be treated for up to 12 months.

A Simon's 2-stage design will be used, assuming that at least a P0 response rate of 10% will be reached for injected lesions. In the first stage, 8 patients will be accrued. If there is > 1 response in these 8 patients, the study will enroll 5 additional patients for a total of 13. The null hypothesis will be rejected if 4 or more responses are observed in 13 patients. This design yields a type I error rate of 0.03 and power of 0.8 when the P1 response rate is 40%.

Study Duration: The duration of the study, defined as interval from when the study opens to enrollment until completion of data analyses, will be 24 months.

Participant Duration: 12 months

1.2 SCHEMA

1.3 SCHEDULE OF ACTIVITIES (SOA)

For explanation of procedures, please see Section 8 (Study Assessments and Procedures).

Baseline evaluations are to be conducted within 1 week prior to start of protocol therapy. Imaging must be done within 4 weeks prior to the start of therapy and then every three months starting at week 12. In the event that the patient's condition is deteriorating, laboratory evaluations should be repeated within 48 hours prior to initiation of the next cycle of therapy.

Table 1: Schedule of Activities

	Wk -4	Wk -1	Wk 1	Wk 2	Wk 3	Wk 4 and Bi-weekly	Wk 12 and every three months	Off Study ^e
T-VEC ^a			X			X	X	
Informed consent		X						
Demographics		X						
Medical history		X						
Concurrent meds		X	X	X	X	X	X	X
Physical exam		X	X			X	X	X
Imaging	X						X	
Vital signs		X	X	X	X	X	X	X
Height		X						
Weight		X	X	X	X	X	X	X
Performance status		X	X			X	X	X
Complete blood panel w/diff, platelets		X	X			X	X	X
CMP ^b		X	X			X	X	X
EKG		X						
Coagulation studies (PT/PTT/INR)		X						
Adverse event evaluation		X	X	X	X	X	X	X
Tumor measurements – ruler/calipers and digital photography of lesions		X	X	X	X	X	X	X
Punch biopsy ^c		X						X
B-HCG blood pregnancy test		X ^d						

a. Talimogene laherparepvec (T-VEC): Dose as assigned; *administration schedule only applies if tumor is visualized*. Dose 2 to be given 21 days after dose 1 with window of +3 days. Window for remaining doses is +/- 3 days.

b. Comprehensive Metabolic Panel: Albumin, alkaline phosphatase, total bilirubin, bicarbonate, BUN, calcium, chloride, creatinine, glucose, , potassium, total protein, SGOT [AST], SGPT [ALT], sodium.

c. Punch biopsy will be performed using a 4-6 mm punch, up to 2 biopsies per instance.

d. Serum pregnancy test (women of childbearing potential) completed within 72 hours of enrollment.

e. Patients will be treated for a maximum of 52 weeks per section 6.1.2.3. Off-study treatment evaluation should be completed within 30 days after last T-VEC treatment. Patients will continue to be followed-up posttreatment to determine RFS and note any complications; patients will also be followed every 6 months (+/- 1 month) for 2 years by telephone, review of follow-up notes for recurrence status and latent herpetic infection.

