8.1.2.4 DURATION OF RESPONSE

Duration of Response

Duration of overall response: The duration of overall response is measured from the time measurement criteria are met for CR or PR (whichever is first recorded) until the first date that recurrent or progressive disease is objectively documented (taking as reference for progressive disease the smallest measurements recorded since the treatment started).

The duration of overall CR is measured from the time measurement criteria are first met for CR until the first date that progressive disease is objectively documented.

Duration of stable disease: Stable disease is measured from the start of the treatment until the criteria for progression are met, taking as reference the smallest measurements recorded since the treatment started, including the baseline measurements.

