8.1.2.5 PROGRESSION-FREE SURVIVAL

Progression-free survival is defined as the duration of time from start of treatment to time of progression or death, whichever comes first.

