8.1.2.6 FOLLOW-UP PERIOD

The study will continue to follow patient's recurrence/vital status and any evidence of latent herpetic infection up to 2 years out from the start of injections, by reviewing routine clinic visit notes and/or telephone contact every six months (see also section 7).

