9.4.3 ANALYSIS OF THE SECONDARY ENDPOINT(S)

For all secondary endpoints except those with time-to-event responses, we will use basic descriptive statistics such as the mean, median, standard deviation and range for continuous variables and frequencies for categorical variables. We will construct exact 95% confidence intervals to describe these secondary endpoints.

For time-to-event responses, we will use Kaplan-Meier estimates and plots to describe the endpoints. Response duration is measured from the time of first injection to initial partial response or complete response. Progression free survival is measured from time of first injection to progression of disease or appearance of new CA, not present at the time of study entry. The median progression-free survival will be reported with 95% confidence interval.

All secondary endpoints are for descriptive purposes, and no power analyses have been performed for them.

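### No definition of response duration counts death, the analysis section defines it as time to response, and post-treatment follow-up is aimed at an undefined RFS

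*Combined protocol and SAP*

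**What the plan says.** **Response duration.** The synopsis and Table 2 use the same words: "Response duration will be measured from the time of initial partial response or complete response until documented progression". Section 8.1.2.4 runs from the first recorded CR or PR "until the first date that recurrent or progressive disease is objectively documented". For complete responders it adds: "The duration of overall CR is measured from the time measurement criteria are first met for CR until the first date that progressive disease" is documented. The analysis section, 9.4.3, says something different: "Response duration is measured from the time of first injection to initial partial response or complete response". None of these texts mentions death.

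**PFS.** Section 8.1.2.5 ends PFS at "time of progression or death, whichever comes first". The synopsis, Table 2 and 9.4.3 end it at progression or new tumors and leave death out.

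**Method.** Section 9.4.3 assigns Kaplan-Meier to the time-to-event endpoints. It gives no censoring rule.

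**Follow-up.** Footnote e to Table 1 in Section 1.3 says: "Patients will continue to be followed-up posttreatment to determine RFS and note any complications". RFS is not in the abbreviation list, the synopsis, Table 2 or Section 9. Section 8.1.2.6 follows "recurrence/vital status and any evidence of latent herpetic infection up to 2 years out from the start of injections". Section 8.1.1 also collects recurrence and vital status, but for up to 2 years from the off-study visit. Footnote e's own list of six-monthly items leaves vital status out. Sections 3 and 9 contain no overall survival endpoint or analysis.

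**The concern.** Kaplan-Meier needs a defined event. If the event is progression or recurrence only, a responder who dies first can enter the curve only as censored. The estimator then treats that patient as someone who could still have progressed later, with the same prospects as the responders still at risk. The curve no longer shows the share of responders who are alive and still in response, which is how a median duration of response is usually read.

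This matters because few responders are expected, so a single death can shift the median. Such deaths are plausible. Section 2.2.1 describes these patients as often elderly, and Section 2.3.1.1 reports that 8 of 10 fatal events in the T-VEC arm of the melanoma phase 3 study were attributed to progression, so 2 were not. That is context from another disease, not a rate for this trial.

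Two further problems bear on the same endpoints. An analyst who programs from 9.4.3 would report a time to response under the label of response duration. And follow-up whose stated purpose is RFS is not tied to the endpoints that need it: PFS and response duration turn on progression, and RFS has no clear meaning for a patient who leaves treatment with tumor still present.

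**Working it through.** **The plan's own figures.** The documents give no figure for response duration, PFS or survival. The only design calculation is the two-stage one in Section 9.2 (8 then 13 patients; stop at 1 or fewer responses, reject the treatment at 3 or fewer). By exact binomial enumeration:

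- Early termination at a 10% response rate: 0.9^8 + 8 × 0.1 × 0.9^7 = 0.8131 (stated 0.813).
- Expected sample size: 8 + (1 − 0.8131) × 5 = 8.93 (stated 8.93).
- Type I error: 0.0307 (stated 0.031). Type II error at 40%: 1 − 0.8015 = 0.1985 (stated 0.198).

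All reproduce, and none depends on how response duration is defined.

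**Number of responders.** At the 40% alternative with all 13 patients treated: 13 × 0.40 = 5.2, so about 5.

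**Size of the overstatement.** Assume constant hazards among responders: λp for progression and λd for death without documented progression. Let f = λd/(λp + λd), the share of first events that are deaths.

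- Median with deaths censored: ln 2/λp.
- Median with deaths counted: ln 2/(λp + λd).
- Ratio: (λp + λd)/λp = 1/(1 − f).

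The documents give no f, so it is an assumption and a range is shown. The last column takes 6.0 months, an illustrative figure, as the median with deaths censored.

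| f | Factor 1/(1−f) | Median with deaths counted |
|---|---|---|
| 0 | 1.00 | 6.0 months |
| 10% | 1.11 | 5.4 months |
| 20% | 1.25 | 4.8 months |
| 30% | 1.43 | 4.2 months |
| 50% | 2.00 | 3.0 months |

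**One death among five responders.** Take invented times of 3, 5, 7, 10 and 14 months, where the patient at 5 months dies without progression and the other four progress.

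- Death censored: S = 0.80 at 3 months, unchanged at 5, then 0.80 × 2/3 = 0.533 at 7, 0.267 at 10 and 0 at 14. The median is 10 months.
- Death counted: S = 0.80, 0.60, 0.40, 0.20, 0. The median is 7 months.

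Neither curve sits exactly at 0.50, so both medians are the same under any usual convention.

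**Follow-up windows.** For a patient treated the full 52 weeks, Section 8.1.2.6 leaves 104 − 52 = 52 weeks of follow-up after treatment. Section 8.1.1 starts its 2 years at the off-study visit, which may fall up to 30 days after the last dose, so up to 52 × 7 + 30 = 394 days after the first injection. The two end dates can therefore differ by about 394 days, or 13 months.

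**The case against.** The other side has real points, and several stronger readings that a reader might infer do not hold.

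- **That vital status feeds no endpoint.** Not supported: Section 8.1.2.5 counts death in PFS. The defect is that the synopsis, Table 2 and 9.4.3 do not.
- **That durability will be overstated.** Not supported as a certainty. It needs a responder to die without documented progression; otherwise the factor is 1.0. The plan states no censoring rule, so censoring of deaths is what the stated event implies, not something the plan says. Under 9.4.3 as written, durability is not measured at all.
- **That progression data stop about 13 months after first injection because later follow-up records only recurrence.** This takes the word too literally. Section 7.1 keeps patients on study procedures after T-VEC stops, Section 8.1.1 allows clinical assessment as well as telephone contact, and Section 8.1.2.4 pairs recurrent with progressive disease.
- **That survival is never reported.** Too broad. Deaths on treatment and for at least 30 days afterwards are reported as serious adverse events (Sections 8.2 and 8.4.5). What is missing is a planned overall survival analysis.

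It can also be said that recurrence is meaningful for complete responders and for resected patients, that a 13-patient response-rate trial need not make survival an endpoint, and that 9.4.3 calls all secondary endpoints descriptive. These points stand. They make the RFS wording on its own a minor matter. They do not supply a death rule for response duration or correct 9.4.3.

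**Conclusion.** The point holds for the secondary endpoints. All four places that define response duration leave death out, one of them describes a different quantity, and the death rule for PFS differs between sections. Median response duration can be overstated by 1/(1−f): nothing at f = 0, 11% at f = 10%, 25% at f = 20%. This rests on constant hazards and on an assumed f, for which the documents give no value. With about 5 responders, one death can move the median by months, as the invented example shows, but the documents cannot say whether such a death will occur.

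The RFS label is undefined and matches no endpoint, the 2-year follow-up window has two starting points, and vital status is collected without a planned survival analysis. The primary response-rate test and its error rates are untouched.

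**What to change.** 1. Use one definition of response duration in the synopsis, Table 2, 8.1.2.4 and 9.4.3: from first CR or PR to progression, recurrence or death from any cause, whichever is first. Censor patients who are alive and event-free at their last disease assessment, not at a later telephone contact. Bring the PFS definitions in the synopsis, Table 2 and 9.4.3 into line with 8.1.2.5. If time to response is also wanted, list it under its own name.
2. In footnote e, replace RFS with the date and basis of progression or recurrence, plus vital status, and use the same items in 8.1.1 and 8.1.2.6. Reconcile the two starting points of the 2-year window.
3. Report overall survival from first injection by Kaplan-Meier, as a description, from the vital status already collected.

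The cost is wording, one data item for the date and basis of progression, and a median response duration that may come out shorter. No new visits are needed.

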2 INTRODUCTION

2.1 STUDY RATIONALE

Talimogene laherparepvec (T-VEC) is an herpes simplex virus type 1- (HSV-1-) based oncolytic virus designed to selectively replicate in tumors and produce granulocyte macrophage colony-stimulating factor (GM-CSF) to stimulate antitumor immune responses. T-VEC is administered by intratumoral injection and is currently under investigation as intralesional therapy for several solid tumor types. Intratumoral injection of T-VEC could result in an influx of infiltrating T cells mediated by direct tumor destruction, potentially initiating an immune response against tumor-associated antigens.

Cutaneous angiosarcoma (CA) is a difficult disease to treat, primarily due to the high recurrence rate and need for wide resection. CA is often associated with a prior history of radiation therapy and can respond well to taxane-based systemic therapy, which has been used effectively in the neoadjuvant setting. Unfortunately, recurrence is experienced by up to 75% of patients, including those treated with combination therapy, and they have no efficacious second-line treatment options available to them. The use of an intralesional immunomodulatory agent like T-VEC represents a novel approach for the treatment of patients whose disease is not controlled by standard therapy and have no other options. An early report of safety using T-VEC in advanced sarcoma patients was presented at ASCO 2018. Three CA patients were enrolled and 2 were classified as responders. The purpose of this trial is to validate this early response signal in a formal phase 2 trial for CA patients.

The goal of injecting T-VEC directly into the tumor is to stimulate both systemic and local anti-tumor responses. The insertion of a GM-CSF gene into the viral genome, as described in Section 2.2.2, will ideally create an adaptive immune response within the tumor, augmenting treatment and furthering the pathway to a complete response of the tumor and hopefully prevention of recurrence of cutaneous angiosarcoma.

2.2 BACKGROUND

2.2.1 DISEASE BACKGROUND

CA is a rare cutaneous neoplasm that is classified as a soft tissue sarcoma which arises within the epidermis or dermis. The disease presents largely as 2 separate phenotypes. In one form, the cause is idiopathic and effects elderly men with a predilection for occurrence in the head and neck region. In another form, the disease is associated with a history of radiation therapy and most commonly affects women, with disease occurring in the skin of the breast after breast conservation therapy for primary breast cancer. The latter form occurs with a median latency period of 7 years between the exposure to radiation and development of a secondary malignancy.

Treatment for either condition is primarily wide surgical resection. Wide margins can be difficult to obtain as anatomic constraints often limit the resection. Even when primary resection is feasible, recurrence is common, with a local recurrence rate up to 60% for those with idiopathic cutaneous angiosarcoma and 75% for those with radiation-associated cutaneous angiosarcoma. Complicating treatment further is the presence of multifocal disease in both the primary and recurrent setting, which is difficult to manage with surgical resection. Despite the known association, radiation therapy has been advocated for cutaneous angiosarcoma as a way to increase local control.

With high local recurrence rates, there is an unmet need for local therapy. The anatomic constraints limiting resection in the primary setting are worse with recurrence and repeat radiation therapy to a site is generally not feasible. Systemic therapy is used for these patients; however, these options are often restricted by the limitations associated with the age of these often elderly patients.

2.2.2 STUDY AGENT

T-VEC (Imlygic), previously known as OncoVexGM-CSF, is a HSV-1–derived oncolytic immunotherapy that selectively replicates within tumors and produces GM-CSF. In talimogene laherparepvec, HSV-1 is modified through deletion of 2 nonessential viral genes, *ICP47* and *ICP34.5*. The deletion of the *ICP47* gene up-regulates the HSV *US11* gene, reduces the suppression of antigen presentation, and enables the virus to grow and replicate within tumor cells. Functional deletion of *ICP34.5* reduces neurotoxicity and enhances tumor-selective replication. The gene encoding GM-CSF is inserted, and its expression promotes dendritic cell activity and increased tumor antigen presentation, potentially inducing greater tumor-specific T cell responses (Figure 1)

[figure not shown]

Figure 1. Local and systemic effects of T-VEC.

T-VEC is administered by direct injection into tumors. For the indications currently FDA-approved in melanoma, an optimized dosing regimen consisting of a first dose of 10^6 plaque-forming units (PFU)/mL (total injected volume dependent on injectable tumor diameter) followed by subsequent doses of 10^8 PFU/mL (total injected volume dependent on injectable tumor diameter) is used. This regimen is based on a phase 1 dose-ranging study (001/01) in which this regimen was identified as being well tolerated by both HSV-1 seronegative and seropositive patients. It is anticipated that this regimen will be used in most other oncology indications going forward, including T-VEC in combination with other treatment modalities.

T-VEC is a modified version of HSV-1. HSV-1 has several advantages over other viruses for development as an oncolytic agent. It infects a wide variety of cell types, has a rapid replication cycle resulting in cell lysis, allows the incorporation of single or multiple inserted genes, which may improve the anti-tumor effect, and appropriate titers can be produced in quantities sufficient for clinical use.

Nonclinical and clinical data have shown that selective deletion of HSV genes results in a nonpathogenic virus with promising properties for cancer therapy. The modifications resulting in the enhanced properties of T-VEC include the following:

- Use of a new isolate of HSV-1 (strain JS1), demonstrated to more effectively lyse a variety of human tumor cell lines in vitro than other viruses used in previous clinical studies.
- Functional deletion of the HSV-1 gene encoding ICP47, improving the presentation of tumor antigens following oncolytic virus replication and intended to enhance the anti-tumor immune response.
- Insertion of the gene encoding human GM-CSF, thereby inducing the differentiation and proliferation of dendritic cell precursors in and around the injected tumor and intended to aid the induction of a systemic anti-tumor immune response.

Multiple safety features have also been incorporated into talimogene laherparepvec, including

- Functional deletion of *ICP34.5*, which functions as a virulence factor during HSV infection. This functional deletion limits replication in non-dividing cells and renders the virus non-pathogenic. The safety of ICP34.5 functionally deleted HSV has been shown in multiple clinical studies.
- Insertion of the human GM-CSF coding sequence such that it replaces all of the gene encoding *ICP34.5* to ensure that any potential recombination events between T-VEC and wild-type virus could only result in a disabled, non-pathogenic virus and could not result in the generation of wild-type virus carrying the gene for human GM-CSF.
- The HSV thymidine kinase (TK) gene remains intact, which renders T-VEC sensitive to anti-viral agents such as acyclovir. Therefore, acyclovir could be used to block virus replication, if necessary, although this has never been found to be needed in the patients treated to date.

T-VEC has been tested for efficacy in a variety of in vitro (cell line) and in vivo murine tumor models and has been shown to eradicate tumors or substantially inhibit their growth at doses comparable to those used in clinical studies. Nonclinical evaluation has also confirmed that GM-CSF enhances the immune response generated, enhancing both injected and uninjected tumor responses, and that increased surface levels of MHC class I molecules result from the deletion of *ICP47*.

